7.8. Genetic Research

The information regarding genetic research is included in [Appendix 8](#).

8. ADVERSE EVENTS AND SERIOUS ADVERSE EVENTS

The investigator or site staff will be responsible for detecting, documenting and reporting events that meet the definition of an AE or SAE as outlined in Section 8.1 and Section 8.2, respectively.

8.1. Definition of an AE

Any untoward medical occurrence in a subject or clinical investigation subject, temporally associated with the use of a medicinal product, whether or not considered related to the medicinal product.

Note: An AE can therefore be any unfavorable and unintended sign (including an abnormal laboratory finding), symptom, or disease (new or exacerbated) temporally associated with the use of a medicinal product. For marketed medicinal products, this

also includes failure to produce expected benefits, abuse, or misuse. Examples of events meeting the definition of an AE include:

- Exacerbation of a chronic or intermittent pre-existing condition including either an increase in frequency and/or grade of the condition
- New conditions detected or diagnosed after study treatment administration even though it may have been present prior to the start of the study
- Signs, symptoms, or the clinical sequelae of a suspected interaction
- Signs, symptoms, or the clinical sequelae of a suspected overdose of either study treatment or a concomitant medication (overdose *per se* will not be reported as an AE/SAE).

“Lack of efficacy” or “failure of expected pharmacological action” *per se* is not to be reported as an AE or SAE. However, any signs and symptoms and/or clinical sequelae resulting from “lack of efficacy” will be reported as an AE or SAE, if they fulfill the definition of an AE or SAE.

Events that **do not** meet the definition of an AE include:

- Medical or surgical procedure (e.g., endoscopy, appendectomy); the condition that leads to the procedure is an AE.
- Situations where an untoward medical occurrence did not occur (social and/or convenience admission to a hospital).
- Anticipated day-to-day fluctuations of pre-existing disease(s) or condition(s) present or detected at the start of the study that do not worsen.
- The disease/disorder being studied, or expected progression, signs, or symptoms of the disease/disorder being studied, unless more severe than expected for the subject’s condition.

8.2. Definition of a SAE

A SAE is any untoward medical occurrence that, at any dose:

- a. Results in death
- b. Is life-threatening

NOTE: The term 'life-threatening' in the definition of 'serious' refers to an event in which the subject was at risk of death at the time of the event. It does not refer to an event, which hypothetically might have caused death, if it were more severe.

- c. Requires hospitalization or prolongation of existing hospitalization

NOTE: In general, hospitalization signifies that the subject has been detained (usually involving at least an overnight stay) at the hospital or emergency ward for observation and/or treatment that would not have been appropriate in the physician’s office or out-subject setting. Complications that occur during hospitalization are

AEs. If a complication prolongs hospitalization or fulfills any other serious criteria, the event is serious. When in doubt as to whether "hospitalization" occurred or was necessary, the AE should be considered serious.

Hospitalization for elective treatment of a pre-existing condition that did not worsen from baseline is not considered an AE.

- d. Results in disability/incapacity, or

NOTE: The term disability means a substantial disruption of a person's ability to conduct normal life functions. This definition is not intended to include experiences of relatively minor medical significance such as uncomplicated headache, nausea, vomiting, diarrhea, influenza, and accidental trauma (e.g. sprained ankle) which may interfere or prevent everyday life functions but do not constitute a substantial disruption.

- e. Is a congenital anomaly/birth defect.
- f. Medical or scientific judgment should be exercised in deciding whether reporting is appropriate in other situations, such as important medical events that may not be immediately life-threatening or result in death or hospitalization but may jeopardize the subject or may require medical or surgical intervention to prevent one of the other outcomes listed in the above definition. These should also be considered serious. Examples of such events are invasive or malignant cancers, intensive treatment in an emergency room or at home for allergic bronchospasm, blood dyscrasias or convulsions that do not result in hospitalization, or development of drug dependency or drug abuse.
- g. All events of possible study treatment-induced liver injury with hyperbilirubinemia defined as ALT ≥ 3 times ULN **and** bilirubin ≥ 2 times ULN ($>35\%$ direct) (or ALT ≥ 3 times ULN and INR >1.5 , if INR is measured) or termed 'Hy's Law' events (INR measurement is not required and the threshold value stated will not apply to subjects receiving anticoagulants).
 - **NOTE:** Bilirubin fractionation is performed if testing is available. If testing is not available, record presence of detectable urinary bilirubin on dipstick indicating direct bilirubin elevations and suggesting liver injury. If testing is unavailable and a subject meets the criterion of total bilirubin ≥ 2 times ULN, then the event is still reported as a SAE. If INR is obtained, include values on the SAE form. INR elevations >1.5 suggest severe liver injury.

8.3. Laboratory and Other Safety Assessment Abnormalities Reported as AEs and SAEs

Any abnormal laboratory test results (hematology, clinical chemistry, or urinalysis), or other safety assessments (e.g., ECGs, radiological scans, vital signs measurements) including those that worsen from baseline, and events felt to be clinically significant in the medical and scientific judgment of the investigator are to be recorded as an AE or SAE, in accordance with the definitions provided.

In addition, an associated AE or SAE is to be recorded for any laboratory test result or other safety assessment that led to an intervention, including permanent discontinuation of study treatment, dose reduction, and/or dose interruption/delay.

Any new primary cancer must be reported as a SAE.

However, any clinically significant safety assessments that are associated with the underlying disease, unless judged by the investigator to be more severe than expected for the subject's condition, are not to be reported as AEs or SAEs.

[figure not shown]
8.3.1. Liver Chemistry Stopping Criteria

Liver chemistry threshold stopping criteria have been designed to assure subject safety and to evaluate liver event etiology during administration of study treatment(s) and the follow-up period (in alignment with the FDA premarketing clinical liver safety guidance).

<http://www.fda.gov/downloads/Drugs/GuidanceComplianceRegulatoryInformation/Guidances/UCM174090.pdf>

[figure not shown]
See [Figure 1](#) and [Figure 2](#) for liver stopping criteria for subjects without and with liver metastases, respectively. The algorithms are best read from left to right.

Figure 1 Phase I/II Liver Chemistry Stopping and Increased Monitoring Algorithm for Subjects WITH entry criteria ALT \leq 2.5xULN

Liver Safety Required Actions and Follow up Assessments Section can be found in [Appendix 3](#)

Figure 2 Phase I/II Liver Chemistry Stopping and Increased Monitoring Algorithm including Subjects WITH documented liver metastases/tumor infiltration at baseline AND entry criteria ALT>2.5xULN but \leq 5xULN

Liver Safety Required Actions and Follow up Assessments Section can be found in [Appendix 3](#)

8.3.1.1. Study Treatment Restart or Rechallenge

If subject meets liver chemistry stopping criteria do not restart/rechallenge subject with study treatment unless:

- GSK Medical Governance approval **is granted**
- Ethics and/or Institutional Review Board (IRB) approval is obtained, if required, and
- Separate consent for treatment restart/rechallenge is signed by the subject

Refer to [Appendix 3](#) for full guidance

8.3.2. Cardiovascular Events

Investigators will be required to fill out event specific data collection tools for the following AEs and SAEs:

- Myocardial infarction/unstable angina
- Congestive heart failure
- Arrhythmias
- Valvulopathy
- Pulmonary hypertension
- Cerebrovascular events/stroke and transient ischemic attack
- Peripheral arterial thromboembolism
- Deep venous thrombosis/pulmonary embolism
- Revascularisation

This information should be recorded in the specific cardiovascular eCRF within one week of when the AE/SAE(s) are first reported.

8.4. Time Period and Frequency of Detecting AEs and SAEs

The investigator or site staff is responsible for detecting, documenting and reporting events that meet the definition of an AE or SAE.

AEs will be collected from the time the first dose of study treatment is administered until 30 days following discontinuation of study treatment regardless of initiation of a new cancer therapy or transfer to hospice.

SAEs will be collected over the same time period as stated above for AEs. In addition, any SAE assessed **as related** to study participation (e.g., protocol-mandated procedures, invasive tests, or change in existing therapy), study treatment or GSK concomitant medication must be recorded from the time a subject consents to participate in the study up to and including any follow-up contact. All SAEs will be reported to GSK within 24 hours, as indicated in Section 8.4.

After discontinuation of study treatment, the investigator will monitor all AEs/SAEs that are ongoing until resolution or stabilization of the event or until the subject is lost to follow-up. At any time after 30 days the investigator may report any AE that they believe possibly related to study treatment.

8.4.1. Method of Detecting AEs and SAEs

Care must be taken not to introduce bias when detecting AEs and/or SAEs. Open-ended and non-leading verbal questioning of the subject is the preferred method to inquire about AE occurrence. Appropriate questions include:

“How are you feeling?” or for pediatric studies, “How does your child seem to feel?”

“Have you had any (other) medical problems since your last visit/contact?” or for pediatric studies, “Has your child had any (other) medical problems or seem to act differently in any way since his/her last visit/contact?”

“Have you taken any new medicines, other than those provided in this study, since your last visit/contact?” or for pediatric studies, “Has your child needed to take any medicines, other than those provided in this study, since his/her last visit/contact?”

8.4.2. Prompt Reporting of SAEs and Other Events to GSK

SAEs, pregnancies, and liver function abnormalities and any other events meeting pre-defined criteria will be reported promptly by the investigator to GSK as described in the following table once the investigator determines the event meets the protocol definition for that event.

Type of Event	Initial Reports		Follow-up Information on a Previous Report	
	Time Frame	Documents	Time Frame	Documents
All SAEs	24 hours	SAE data collection tool	24 hours	Updated SAE data collection tool
“CV events” and/or “death”	Initial and follow up reports to be completed within one week of when the cardiovascular event or death is reported	“CV events” and/or “death” data collection tool(s) if applicable	Initial and follow up reports to be completed within one week of when the cardiovascular event or death is reported	Updated “CV events” and/or “death” data collection tool(s) if applicable
Pregnancy	2 Weeks	Pregnancy Notification Form	2 Weeks	Pregnancy Follow-up Form
Liver chemistry abnormalities (Section 8.3.1):				
ALT \geq 3 times ULN and bilirubin \geq 2 times ULN ($>35\%$ direct) (or ALT \geq 3 times ULN and INR >1.5 , if INR is measured) ^c	24 hours ^a	SAE data collection tool; Liver Event eCRF and liver imaging and/or biopsy eCRFs if applicable ^b	24 hours	Updated SAE data collection tool. Updated Liver Event eCRF ^b
ALT \geq 5 times ULN; ALT \geq 3 times ULN with hepatitis or rash or 3 times ULN \geq 4 weeks	24 hours ^a	Liver Event eCRF ^b	24 hours	Updated Liver Event eCRF ^b
ALT \geq 3 times ULN and <5 times ULN and bilirubin <2 times ULN	24 hours ^a	Liver Event eCRF does not need to be completed unless elevations persist for 4 weeks or subject cannot be monitored weekly for 4 weeks ^b		

- a. GSK to be notified at onset of liver chemistry elevations to discuss subject safety.
- b. Liver event documents should be completed as soon as possible
- c. INR measurement is not required; if measured, the threshold value stated will not apply to subjects receiving anticoagulants.

Methods for detecting, recording, evaluating, and following up on AEs and SAEs are provided in the SPM.

8.4.3. Regulatory reporting requirements for SAEs

Prompt notification of SAEs by the investigator to GSK is essential so that legal obligations and ethical responsibilities towards the safety of subjects are met.

GSK has a legal responsibility to notify both the local regulatory authority and other regulatory agencies about the safety of a product under clinical investigation. GSK will comply with country specific regulatory requirements relating to safety reporting to the regulatory authority, IRB/EC and investigators.

Investigator safety reports are prepared for suspected unexpected serious adverse reactions according to local regulatory requirements and GSK policy and are forwarded to investigators as necessary.

An investigator who receives an investigator safety report describing a SAE(s) or other specific safety information (e.g., summary or listing of SAEs) from GSK will file it with the IB and will notify the IRB/EC, if appropriate according to local requirements.

9. CONCOMITANT MEDICATIONS AND NON-DRUG THERAPIES

Subjects will be instructed to inform the investigator prior to starting any new medications from the time of first dose of study treatment until the end of the study (Final Study Visit). Any concomitant medication(s), including non-prescription medication(s) and herbal product(s), taken during the study will be recorded in the eCRF. Additionally, a complete list of all prior anti-cancer therapies will be recorded in the eCRF.

If future changes are made to the list of permitted/prohibited medications, formal documentation will be provided by GSK and stored in the study file. Any such changes will be communicated to the investigative sites in the form of a letter.

9.1. Permitted Medications

Subjects should receive full supportive care during the study, including transfusions of blood and blood products, and treatment with antibiotics, antiemetics, antidiarrheals, and analgesics, and other care as deemed appropriate and in accordance with their institutional guidelines and considering the list of contra-indicated medicines included in Section 9 of the protocol.

Palliative radiation and/or surgical intervention is permitted after discussion with the GSK medical monitor and documenting the treatment in the eCRF.

Questions regarding concomitant medications should be directed to the GSK Medical Monitor for clarification.

9.2. Prohibited and Cautionary Medications

Subjects should not receive those medications listed as prohibited in Section [9.2](#)

Subjects should not receive other anti-cancer therapy including chemotherapy, radiation therapy, immunotherapy, biologic therapy, investigational therapy, hormone therapy (other than leuprolide or other GnRH agonists for mCRPC), surgery or tumour embolization while on treatment in this study. Other anti-cancer therapy should not be administered unless one of the following occurs: documented disease progression; unacceptable or unmanageable toxicity; subject is withdrawn from the study at the investigator's discretion or consent is withdrawn; or no further clinical benefit is anticipated which requires permanent discontinuation of study drug. .

Concurrent use of therapeutic warfarin may be allowed. However, increased monitoring of INR and bleeding with dose titration for warfarin is recommended due to potential increase in warfarin concentration when administered with study treatment GSK2816126. Anticoagulants that do not have reversal agents available are prohibited from 14 days prior to the first dose of study drug through completion of the Final Study Visit.

9.2.1. Drugs that may alter the Pharmacokinetics of GSK2816126

It has been demonstrated in vitro that GSK2816126 is metabolized by CYP3A enzymes. However, turnover in human liver microsomes and hepatocytes was low and the relative contribution of this pathway to the elimination of GSK2816126 is presently unknown. GSK2816126 has also been shown to be a substrate of P-gp and BCRP transporters. .

Therefore, substances that potently inhibit or induce CYP3A, P-gp or BCRP ([Table 9](#)) should be avoided during the course of the study where possible as these drugs could lead to higher/lower exposure in subjects, potentially leading to alterations of the pharmacologic effects of GSK2816126.

The impact of inhibition of P-gp or BCRP on GSK2816126 pharmacokinetics has not been assessed in humans. Drugs that are mild to moderate inhibitors of P-gp and BCRP should be administered with caution because they may alter GSK2816126 levels ([Table 10](#)).

Table 9 Prohibited Drugs Potentially Affecting GSK2816126 Pharmacokinetics Resulting in Increased or Decreased GSK2816126 Exposure

PROHIBITED – strong inducers/inhibitors of CYP3A, Pgp, Bcrp, since levels of GSK2816126 may be decreased/increased	
Strong CYP3A/Pgp/Bcrp Inhibitor/Inducer	Therapeutic Area
clarithromycin, telithromycin, rifamycin class agents (e.g. rifampin, rifabutin, rifapentine) troleandomycin	Antibiotics
itraconazole, ketoconazole	Antifungals
Nefazodone	Antidepressants
Amprenavir, atazanavir delavirdine, fosamprenavir indinavir, lopinavir, nelfinavir, ritonavir, saquinavir, tipranavir	Antiretrovirals, Protease Inhibitors
carbamazepine, cyclosporine, phenobarbital, amiodarone	Miscellaneous

Table 10 Use with Caution Drugs Potentially Affecting GSK2816126 Pharmacokinetics Resulting in Increased or Decreased GSK2816126 Exposure

USE WITH CAUTION – Potential for Inducers/inhibitors of CYP3A, Pgp and BCRP since levels of GSK2816126 may be decreased/increased	
Mild/Moderate CYP3A or Pgp Inhibitor/Inducer	Therapeutic Area
voriconazole	Antifungal
diltiazem, verapamil	Antiarrhythmics
Cortisone (>50 mg), hydrocortisone (>40 mg), prednisone or prednisolone (>10 mg), methylprednisolone or triamcinolone (>8 mg), betamethasone or dexamethasone (>1.5 mg)	Glucocorticoids (oral)
aprepitant, cimetidine, montelukast,	Miscellaneous
1. NOTE: Topical or inhaled steroids are permitted.	

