9.3. Drugs that may have their Pharmacokinetics altered by GSK2816126

The potential for pharmacokinetic interactions with drugs likely to be co-administered with GSK2816126 in vivo has not been assessed. In vitro data suggests that GSK2816126 has the potential to inhibit CYP2C8, CYP2C9, CYP2C19, and CYP3A (IC₅₀'s <9 μM). GSK2816126 does not appear to be an inhibitor of CYP1A2 or CYP2D6. GSK2816126 is also an in vitro inhibitor of human transporters BCRP, OATP1B1, OATP1B3, OCT2, MATE1 and MATE2-K (IC₅₀ values of 21, 13, 34, 2.88, 0.025 and 0.95 μM, respectively) In addition, GSK2816126 was shown to activate human PXR (EC₅₀ = 6.3 μM) and, therefore, may have the potential to induce CYP enzymes. A further in

vitro study showed induction of CYP3A4 mRNA with a calculated EC₅₀ of 4.22-5.43 µM and E_{max} of 3.22-16.5-fold.

These results suggest that narrow therapeutic index medications that are substrates of CYP2C8, CYP2C9, CYP2C19 and CYP3A4, and/or transporters BCRP, OATP, OCT2, MATE1 and MATE2-K should be prohibited as their levels may be increased, and could lead to adverse effect (Table 11). Co-administration of sensitive substrates of these CYPs and/or transporters should be **used with caution** as their levels may be increased or decreased (Table 11). Discussion by the PI/staff with the GSK medical monitor(s) must occur before use of these drugs.

Table 11 Prohibited Drugs Potentially Affected by GSK2816126

PROHIBITED – highly sensitive and/or low therapeutic index CYP3A/CYP2C8/CYP2C9/CYP2C19/OCT2/MATE substrates since levels of these drugs may be increased	
CYP3A Substrate	Therapeutic Area
alprazolam, diazepam, midazolam, triazolam	Hypnotics and Sedatives
diergotamine, ergotamine, eletriptan	Antimigraine agents
pimozide,	Antidepressant, Antipsychotics, Antianxiety agents
cyclosporine, sirolimus, tacrolimus	Immunosuppressive agents
astemizole	Antihistamine
sildenafil, tadalafil, vardenafil	Erectile Dysfunction agents
eplerenone	Selective Aldosterone Blockers
tizanidine	Muscle Relaxant
quinidine	Antiarrhythmics
CYP2C8, CYP2C9 and CYP2C19 Substrate	
Amiodarone	Antiarrhythmics
Paclitaxel	Anticancer
tolbutamide, nateglinide	Antidiabetic
phenytoin, s-mephénytoin	Anticonvulsants
acenocoumarol	Anticoagulant
Cyclophosphamide	Immunosuppressant
OCT2, MATE1, MATE2-K Substrate	
Cisplatin	Anticancer

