Dofetilide, pilsicainide, procainamide	Antiarrhythmics

Table 12 Use with Caution - Drugs Potentially Affected by GSK2816126

USE WITH CAUTION – Monitor for side effects since levels of these drugs may be increased. Consider dose reduction.	
CYP2C8/9/19/3A/OATP1B1/OATP1B3 Substrate	Therapeutic Area
felodipine	Calcium Channel Blockers
lovastatin, rosuvastatin, atorvastatin, fluvastatin	HMG-CoA Reductase Inhibitors
oral budesonide	Corticosteroids
fentanyl, alfentanil	Analgesics
Warfarin*, cilostazole	Anticoagulants and Antiplatelets
Rosiglitazone, repaglinide	Antidiabetics
OCT2, MATE1, MATE2-K Substrate	
captopril	Anti-Hypertensive
ganciclovir, tenofovir	Antiviral
 gabapentin,	Anticonvulsants
certirizine, ranitidine	H2 Blocker
metformin	Antidiabetics
atecegatran metoxil	Anticoagulants
glycopyrronium	Respiratory, COPD
pindolol, triamterene	Antihypertension
varenicline	Others
USE WITH CAUTION – Monitor for loss of efficacy or substitute another medication	
Substrates of CYP3A4/CYP2B6 that are affected by induction	Therapeutic Area
doxycycline, chloramphenicol,	Antibiotics
caspofungin, terbinafine	Antifungals
enalapril, diltiazem, amlodipine, nifedipine, nisoldipine	Antihypertensives
amitriptyline, nortriptyline, desipramine, imipramine, protriptyline, clomipramine, doxepin	Antidepressants
glipizide, glyburide, tolazamide, chlorpropamide	Antidiabetics
zonisamide, valproate, divalproex	Anticonvulsants
buspirone	Antidepressant, Antipsychotics, Antianxiety agents
buprenorphine, naloxone, naltrexone, nalmefene	Opioid agonist/antagonists
aprepitant, clofibrate, tramadol, methohexitol, estazolam, galantamine, leflunomide, solifenacin, sulfasalazine,	Miscellaneous

*Concurrent use of therapeutic warfarin may be allowed. Increased monitoring of INR and bleeding with dose titration of warfarin is recommended due to potential increase in warfarin concentration when co-administered with GSK2816126. However, anticoagulants that do not have reversal agents available are prohibited

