Chloroquine	Anti-malarial	Levosulpiride (only on non US Market)	Antipsychotic
Chlorpromazine	Anti-psychotic / Anti-	Mesoridazine	Anti-psychotic

Generic Name	Drug Class	Generic Name	Drug Class
	emetic	(Removed from Market)	
Cilostazol	Phosphodiesterase 3 inhibitor	Methadone	Opiate
Ciprofloxacin	Antibiotic	Moxifloxacin	Antibiotic
Cisapride (Removed from Market)	GI stimulant	Ondansetron	Anti-emetic
Citalopram	Anti-depressant, SSRI	Oxaliplatin	Antineoplastic Agent
Clarithromycin	Antibiotic	Papaverine HCL (Intra-coronary)	Vasodilator, Coronary
Cocaine	Local anesthetic	Pentamidine	Antibiotic
Disopyramide	Anti-arrhythmic	Pimozide	Anti-psychotic
Dofetilide	Anti-arrhythmic	Probuconol (Removed from Market)	Antilipemic
Domperidone (Only on non US Market)	Anti-nausea	Procainamide	Anti-arrhythmic
Donepezil	Cholinesterase inhibitor	Propofol	Anaesthetic, general
Dronedarone	Anti-arrhythmic	Quinidine	Anti-arrhythmic
Droperidol	Anti-psychotic / Anti-emetic	Roxithromycin (Only on Non US Market)	Antibiotic
Erythromycin	Antibiotic	Sevoflurane	Anesthetic, general
Escitalopram	Anti-depressant, SSRI	Sotalol	Anti-arrhythmic
Flecainide	Anti-arrhythmic	Sparfloxacin (Removed from Market)	Antibiotic
Fluconazole	Antifungal	Sulpiride (Only non US Market)	Anti-psychotic, atypical
Gatifloxacin (Removed from Market)	Antibiotic	Sulpiride (Only on Non US Market)	Anti-psychotic, atypical
Grepafloxacin (Off market worldwide)	Antibiotic	Terlipressin (Only on non US Market)	Vasoconstrictor
Halofantrine	Anti-malarial	Terfenadine (Removed from US Market)	Antihistamine
		Thioridazine	Anti-psychotic
		Vandetanib	Anti-cancer

Data Source: www.crediblemeds.org (9 January 2017)

Table 14 Drugs Known to prolong the QT interval with a Possible Risk of Torsades de Pointes that are Permitted for co-administration with Extreme Caution

Generic Name	Drug Class	Generic Name	Drug Class
Alfuzosin	Alpha1-blocker	Mirabegron	Beta3 adrenergic antagonist
Apomorphine	Dopamine agonist	Mirtazapine	Anti-depressant, Tetracyclic
Aripiprazole	Anti-psychotic, atypical	Moexipril/HCTZ	Anti-hypertensive
		Nicardipine	Anti-hypertensive
Artemether+piperaquine	Antimalarial	Nilotinib	Kinase inhibitor
Asenapine	Anti-psychotic, atypical	Norfloxacin	Antibiotic
Atomoxetine	Norepinephrine reuptake inhibitor	Nortriptyline	Antibiotic
Bedaquiline	Antibiotic	Ofloxacin	Antibiotic
Bendamustine	Alkylating agent		
Bortezomib	Proteasome inhibitor	Osimertinib	Tyrosine kinase inhibitor
Bosutinib	Tyrosine kinase inhibitor	Oxytocin	Oxytocic

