Buprenorphine	Opioid receptor modulator	Paliperidone	Anti-psychotic, atypical
Capecitabine	Anticancer	Panobinostat	Histone deacetylase inhibitor
Ceritinib	Kinase inhibitor	Pasireotide	Somatostatin analog
Clomipramine	Antidepressant, Tricyclic	Pazopanib	Tyrosine kinase inhibitor
Clozapine	Anti-psychotic, atypical	Perflutren lipid microspheres	Imaging contrast agent
Crizotinib	Kinase inhibitor	Perphenazine	Antipsychotic
Cyamemazine (cyamepromazine)(Only on Non US Market)	Antipsychotic	Pipamperone (On non US Market)	Antipsychotic
Dabrafenib	Anti-cancer	Promethazine	Anti-psychotic / Anti-emetic
Dasatinib	Tyrosine kinase inhibitor		
Degarelix	Gonadotropin Releasing Hormone		
Delamanid (Only on Non US Market)	Antibiotic	Rilpivirine	Anti-viral
Desipramine	Antidepressant, Tricyclic	Risperidone	Anti-psychotic, atypical
Dexmedetomidine	Sedative		
		Romidepsin	Histone deacetylase inhibitor
Dolasetron	Anti-emetic	Saquinavir	Anti-viral
Efavirenz	Antiretroviral	Sertindole (On non US Market)	Anti-psychotic, atypical
Eribulin mesylate	Anti-cancer	Solifenacin	Muscle Relaxant
Ezogabine (Retigabine)	Anticonvulsant	Sorafenib	Tyrosine kinase inhibitor
Famotidine	H2-receptor antagonist	Sunitinib	Anti-cancer
Felbamate	Anti-convulsant		
Fingolimod	Sphingosine phosphate receptor modulator	Tamoxifen	Anti-cancer

Generic Name	Drug Class	Generic Name	Drug Class
Flupentixol (Only on Non US Market)	Dopamine 2 and 5HT2a antagonist	Telavancin	Antibiotic
Foscarnet	Anti-viral	Telithromycin	Antibiotic
		Tetrabenazine	Monoamine Transporter Inhibitor
		Tiapride (Only on Non US Market)	Selective D2, D3 dopamine antagonist
Gemifloxacin	Antibiotic	Tizanidine	Muscle relaxant
Granisetron	Anti-emetic	Tolterodine	Muscle relaxant
Hydrocodone-ER	Analgesic	Toremifene	Estrogen agonist/antagonist
Iloperidone	Anti-psychotic, atypical	Trimipramine	Antidepressant, Tricyclic
Imipramine (melipramine)	Antidepressant, Tricyclic	Tropisetron (only on Non US Market)	Antiemetic
Isradipine	Anti-hypertensive	Vardenafil	Phosphodiesterase inhibitor
Lapatinib	Anti-cancer	Vemurafenib	Kinase Inhibitor
Lenvatinib	Anticancer	Venlafaxine	Anti-depressant, SNRI
Leuprolide	Gonadotropin Receptor Anonist	Vorinostat	Histone deacetylase inhibitor
Lithium	Anti-mania		
Melperone (Only on Non US Market)	Antipsychotic, atypical	Zotepine (Only on Non US Market)	Anti-psychotic, atypical
Mifepristone	Progesterone antagonist		

Data Source: www.crediblemeds.org (9 January 2017)

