If a subject requires medication for hyperemesis, due to the potential of serotonin 5-HT3 receptor antagonists to increase QTcF, palonosetron and ondansetron at a maximum oral dose of 8 mg TID are the only allowed drugs in this class. Intravenous administration of these drugs are not permitted.

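### Five drugs are prohibited in one Section 9 table and allowed with caution in another, and the protocol does not say which listing prevails

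*Protocol*

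**What the plan says.** The Protocol regulates concomitant medication through six tables in Section 9, grouped by type of risk.

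- **Section 9.2.1, effect of other drugs on GSK2816126.** The prohibited list is headed "Table 9 Prohibited Drugs Potentially Affecting GSK2816126 Pharmacokinetics". Its antibiotics row includes "clarithromycin, telithromycin, rifamycin class agents" and its antiretroviral row includes "nelfinavir, ritonavir, saquinavir, tipranavir". Table 10 is the matching caution list.
- **Section 9.3, effect of GSK2816126 on other drugs.** Table 11 (prohibited) includes "sildenafil, tadalafil, vardenafil" and, in a separate row, tizanidine. Table 12 (use with caution) includes "Warfarin*, cilostazole".
- **Section 9.4, QT prolongation.** Table 13 (prohibited) includes cilostazol and ondansetron, neither with a qualifier. Table 14 covers drugs "with a Possible Risk of Torsades de Pointes that are Permitted for co-administration with Extreme Caution" and lists "Telithromycin", saquinavir, tizanidine, vardenafil, granisetron, dolasetron and tropisetron.
- **Antiemetic paragraph after Table 14.** It says that palonosetron and ondansetron, with an oral dose limit, "are the only allowed drugs in this class", and it bars intravenous use.

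Exclusion criterion 5 (Section 5.2.3) excludes anyone using, or expected to need, a prohibited medication, and points to Section 9 as a whole. The risk table in Section 1.3.1 names these restrictions as mitigation for QT prolongation and for drug interactions.

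**The concern.** A drug that is prohibited under one heading and permitted under another has no single status. Eligibility depends on that status through exclusion criterion 5. Section 5.2.3 allows no deviation from the exclusion criteria, and Section 3.2 allows no waivers. The same lists govern what a subject may take on study, and they are part of the stated control of QT and interaction risk. A site that consults only one table finds a clear answer there and sees no sign that another table says the opposite.

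**Working it through.** No sample size, power or error rate is involved. The check compares the lists.

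**Step 1: table against table.** Each prohibited table (9, 11, 13) was compared with each caution or permitted table (10, 12, 14), which gives 3 × 3 = 9 pairs. Three pairs share entries:

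| Pair | Shared drugs | Status in first | Status in second |
|---|---|---|---|
| 9 and 14 | telithromycin, saquinavir | prohibited | permitted, extreme caution |
| 11 and 14 | tizanidine, vardenafil | prohibited | permitted, extreme caution |
| 13 and 12 | cilostazol (spelled cilostazole in Table 12) | prohibited | use with caution |

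The other six pairs (9/10, 9/12, 11/10, 11/12, 13/10, 13/14) share none. The total is 2 + 2 + 1 = 5 drugs. Clarithromycin, in the same Table 9 row as telithromycin, is not in conflict, because Tables 9 and 13 both prohibit it.

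**Step 2: is there a precedence rule?** None is stated, and plausible rules give different answers for the five drugs:

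- If the QT tables prevailed, four would be permitted with extreme caution and cilostazol prohibited.
- If the interaction tables prevailed, those four would be prohibited and cilostazol usable with caution.
- If the stricter listing prevailed, all five would be prohibited.

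Nearby text does not settle it. Section 9.2 refers only to drugs prohibited in Section 9.2, while Tables 11 and 13 are in 9.3 and 9.4. The text of 9.2.1 asks sites to avoid Table 9 drugs where possible, which is softer than the table heading. Section 9.3 cites Table 11 for its caution group, although that group is in Table 12.

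**Step 3: tables against the antiemetic paragraph.** Four 5-HT3 antagonists do not match it. Granisetron, dolasetron and tropisetron are permitted in Table 14 but fall outside the two drugs the paragraph allows. Ondansetron is prohibited in Table 13 with no oral exception, while the paragraph allows it orally. Here the paragraph names the class and gives its reason, so it reads as a specific rule qualifying general tables. The Amendment 4 summary also mentions the oral allowance, which suggests it was intended.

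**The case against.** The strongest reply is that the tables answer different questions. Table 9 concerns exposure to the study drug, Tables 11 and 12 exposure to the other drug, and Tables 13 and 14 torsades risk only. On this view a Table 14 entry means only that QT risk alone does not bar the drug, and a prohibition made for another reason stands. Exclusion criterion 5 points to all of Section 9 without a carve-out, which fits a strictest-listing reading. In addition, Sections 9.1 and 9.4 send medication questions to the Medical Monitor, and Section 9.3 requires that discussion before its caution-class substrates are used, which would include cilostazol under Table 12.

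Much of this stands, and it reduces the practical effect. It does not remove the contradiction: the strictest-listing reading is nowhere written, Table 14 is titled as a permission, and a site that sees one clear entry has no reason to ask.

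Three stronger inferences are tempting but unsupported.

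- **That sites cannot apply the rule.** A workable reading and a consultation route both exist.
- **That eight or nine drugs carry opposite statuses between the tables.** Only five do. The four 5-HT3 entries conflict with a paragraph that largely settles them.
- **That the conflict adds noise to the QT and DLT data.** The documents give no frequency of use for these drugs and no figure that would support this.

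**Conclusion.** Five drugs have contradictory statuses in the current Section 9 tables, with no stated precedence. Four 5-HT3 entries also need to be brought into line with the antiemetic paragraph. This is wrong as written and should be corrected, because eligibility and a named risk control rest on the lists. Its reach is narrow: the two QT tables share no drug with each other, and saquinavir matters little in practice because it is listed as an antiretroviral and known HIV is excluded (exclusion criterion 6). The conclusion rests on the table entries as printed and on reading cilostazole as cilostazol. It takes no position on the right status for any drug.

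**What to change.** Reconcile Tables 9, 11, 12, 13 and 14 so that each of the five drugs has one status, decided by the clinical team. Add one sentence stating which listing governs when a drug is on both an interaction list and a QT list. Reconcile the ondansetron entry in Table 13 and the granisetron, dolasetron and tropisetron entries in Table 14 with the antiemetic paragraph, by edit or footnote. Keep the Medical Monitor route for questions the lists do not answer.

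The cost is a table edit and a letter to sites. Section 9 already provides for changes to the permitted and prohibited lists by documented letter. Sample size and analysis are unaffected.
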